### 2. SCHEMA

Study sequence is shown above for all steps following informed consent in Visit 1.

- Subjects who meet the inclusion criteria are first asked to keep a symptom diary for two weeks to determine whether they have an adequate amount of staining, solid or liquid fecal incontinence to be enrolled. The number of FI episodes during baseline will become the reference for judging whether they demonstrate a 75% reduction in the frequency of FI. For patients who have a variable pattern of FI and the investigator believes that the initial two-week diary data collection did not adequately capture the extent of the FI, then the baseline bowel diary may be kept by the patient for an additional two weeks.
- 2. Subjects who have an adequate amount of FI during baseline and who fulfill other inclusion criteria are enrolled in a 4-week EMM protocol to determine whether this will reduce their FI episodes by 75% or more. If it does, they are not included in the randomized trial but are scheduled to return at 3 months for a follow-up assessment. If the subject does not achieve at least a 75% reduction in FI, they are randomized to one of two therapies: BIO or INJ. Whether or not participants are EMM responders, data regarding ongoing adherence to the EMM prescriptions will be collected from participants at the end of the 1-month EMM period and then also at the 3-; 6-; 12-; and 24-month follow-up assessments.
- 3. Each treatment intervention follows a printed protocol document. The number of treatment visits varies somewhat, from 2-3 visits for INJ, and 5-6 visits for BIO.

At 3 months, all subjects who received a randomized therapy are assessed to determine whether they meet the criteria for treatment success. If they fail to demonstrate a 75% decrease in FI compared to baseline, they are labelled as treatment failures and are offered the opportunity to try the other randomization treatment or SNS. Those subjects who were initial responders to EMM but who are determined at 3 months follow-up to no longer be responding to EMM will be eligible to be randomized to one of the two treatment therapies (BIO or INJ). For all participants, follow-up assessments occur at 6, 12, 18 and 24 months. The 3-, 6-, 12 and 24-month follow-up assessments may be completed in-person or remotely. The more limited follow-up data collection at 18-month should always be collected during a telephone call.

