- C. Identify baseline predictors of responsiveness to each intervention and the mechanistic basis for each treatment. Candidate predictors are (a) demographic variables (e.g., sex, age, race, ethnicity, education); (b) clinical history variables (e.g., FI frequency, volume, duration, and association with urgency and diarrhea); and (c) baseline pelvic floor physiology (e.g., anal canal resting pressure, squeeze pressure, duration of squeeze, rectal sensory threshold for first sensation and urgency, maximum tolerable volume, structural integrity of anal sphincters assessed by ultrasound, and integrity of the pelvic floor innervation by trans-sacral and trans-lumbar magnetic evoked potentials).

- D. Evaluate treatment combinations. Patients who do not meet the responder criterion by 3 months follow up will be offered the option of choosing additional therapy. This constitutes a pragmatic clinical trial which mimics clinical practice and will provide preliminary data for a future study. A second reason for allowing patients to add an additional preferred treatment if they do not show at least a 75% improvement is to facilitate recruitment; in our feasibility survey, subjects told us that the opportunity to try another treatment if the first failed would increase their willingness to be randomized. Data analysis will estimate 95% confidence intervals for the percent of responders to each treatment combination and to each monotherapy, and differences in responder rates between groups will be assessed.
  - Research objective 4. To compare the improvement in FI after combination treatment versus monotherapy and compare improvement among various treatment combinations, up to 24 months after administration of each treatment combination, compared to monotherapy.
  - Research objective 5. To estimate differences in the magnitude of improvement in FI from baseline to end of treatment between the treatment combinations.
- E. Assess the efficacy and durability of enhanced medical treatment and identify patient characteristics that predict treatment response.
  - Research objective 6. To estimate the responder rate during the last two weeks of enhanced medical treatment and also during follow up at 3, 6, 12, and 24 months.
  - Research objective 7. To assess the proportion of patients reporting AEs of pelvic pain of grade II or higher, or SAEs requiring hospitalization, during all weeks of medical treatment.

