Previous studies have identified a number of limitations to paper diaries: (1) Missing data if subjects forget to complete the diary or if it is illegible. (2) Inaccurate data that may result if subjects forget to record events when they occur and then try to remember what happened at the end of the day or several days later. In previous studies, we provided patients with a pocket-sized paper diary to take with them throughout the day and asked them to transfer their symptom ratings from the paper diary to a website at the end of the day. If they failed to submit a report to the website within 12 hours, they were sent an email reminder or were telephoned. They were also reminded the next time they attempted to enter data, if the data for the previous day was missing, and they were given an opportunity to report on the previous day; however, they were not permitted to go back further than the previous 24 hours. They were also provided with bonus payments for not missing any diary reports. With this combination of techniques, we were able to obtain an average of 73 consecutive days of symptom diaries without interruption from 185 IBS patients varying in age from 18 to 84. However, there is concern that since advancing age is a risk factor for FI, the patients who enroll in this study will be older and less comfortable than young or middle-aged subjects with transferring data to the internet. Therefore, to avoid biasing enrollment against these older subjects, we decided to use paper diaries for this study. To ameliorate potential problems with missing or untimely data reporting we will (1) thoroughly train subjects in recording their diary information at enrollment, and (2) telephone subjects during the first two weeks that they keep the diary to ensure that they are able to record events on this paper diary when they occur.

To protect against experimenter bias, patients will be classified as responders or non-responders based on diary data entered into the electronic data capture (EDC) system at the end of EMM and at 3-, 6-, 12-, and 24-month follow-up. Once the diary data are entered, a calculation performed within the EDC system will determine which patients are non-responders eligible for randomization, and the same process will determine which patients are non-responders at 3 months so they can be offered alternative treatment.

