#### 5.4 Estimated patient flow for this study

Figure 3 shows the estimated flow of patients through this study and identifies our assumptions regarding attrition. We estimate we will need to screen 855 patients because 2/3 will be ineligible or unwilling to be randomized. This leaves 285 to be recruited into the EMM protocol. Based on the Heymen study, we assume

15% attrition during this treatment phase and also assume that 20% (n=57) will be responders to EMM and therefore not eligible for randomization. This will leave 194 to be randomized (97 per group).

Figure 3 shows that we expect 78 from the BIO group to complete the 3-month assessment after allowing for attrition of 20% and we expect 92 from the INJ group to complete the 3-month assessment. (We assume attrition will be no greater than 5% for the INJ group because this is a low-burden treatment and also because patients will want to be screened for AEs related to INJ.) However, the statistical analysis will be by intent to treat (ITT) and will include all 194 randomized to treatment; patients who are lost to follow up prior to 3 months will be considered treatment failures. The number of patients we expect to be responders to each of the treatments at the 3-month assessment is based on the pivotal trials shown in Table 1. We separated them in this way in Figure 3 to be able to estimate the numbers of non-responders who are likely to choose an additional treatment option after 3 months. The expected number of non-responders eligible for an additional therapy at 3 months is 63 for the INJ arm^16 and 17 for the biofeedback arm^15. Assuming equal probability of choosing either of the 2 available options as an added or alternative treatment, we could expect 40 patients to choose the SNS treatment, 32 to choose BIO, and 9 to choose INJ. For the primary analyses of follow up at 6, 12 and 24 months, these non-responders will be retained in the ITT analysis as non-responders to their primary assignment at randomization. However, when we perform exploratory analyses of treatment combinations, these subjects will be treated as distinct groups and compared to patients who received monotherapy for the duration of the study. These comparisons (Aim D) are exploratory because there is insufficient power to test for significance. The left column of boxes in Figure 3 shows how we intend to follow up the responders to EMM.

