Assess the efficacy and durability of enhanced medical treatment and identify patient characteristics that predict treatment response. The proportion of responders will be calculated at the end of EMM and at 3-, 6-, 12-, and 24-month follow-up. A longitudinal generalized linear model will be constructed to predict treatment response based on time and clinical site; the model will account for the lack of independence between multiple measures assessed over time on the same study participant by modeling the within-participant covariance structure. Participants who are non-responders to EMM at 3 months will continue to be classified as non-responders at 6, 12, and 24 months. Participants without a valid bowel diary will be classified as non-responders at that time point, and those who initiate off-study treatment for FI after EMM will be classified as non-responders at each subsequent visit/assessment. Using this model, we will compare response rates at the end of EMM to response rates at 3, 6, 12, and 24 months. We will also calculate 95% confidence intervals for the percentage of participants reporting AEs during EMM. Costs of EMM will be estimated and compared to costs of the other study interventions using methods described for cost of care analysis. The predictors of response to EMM at baseline, 3, 6, 12, and 24 months will be explored using generalized linear modeling.

*Cost- Effectiveness Analysis.* We will estimate the impact of each intervention on quality-adjusted life-years (QALYs). QALYs are summary measures of morbidity and mortality that typically range from 0 to 1 over a full year, where 1 represents perfect health. QALY estimates will be obtained from the EQ-5D; annual QALY measures will be calculated. We will assess the average cost per QALY gained for each intervention and the incremental cost per QALY gained by comparing the interventions ordered from lowest to highest QALY gains (i.e., comparing the intervention with medium effectiveness to the intervention with lowest effectiveness and the intervention with highest effectiveness to the intervention with medium effectiveness).

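### The planned EMM durability comparison uses as its reference the diary that selects who stays on EMM, so a fall appears even if the benefit is fully maintained

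*Combined protocol and SAP*

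**What the plan says.** Section 8.3 describes one longitudinal model for EMM response with time and clinical site as predictors. "The proportion of responders will be calculated at the end of EMM and at 3-, 6-, 12-, and 24-month follow-up", and from the model "we will compare response rates at the end of EMM to response rates at 3, 6, 12, and 24 months".

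The first of these rates comes from the end of the run-in. Objective 6 in Section 1.1 is "To estimate the responder rate during the last two weeks of enhanced medical treatment" and during later follow-up. Section 4.1.1 says of the diary data entered at that point that "a calculation performed within the EDC system will determine which patients are non-responders eligible for randomization". The Schema in the Protocol Summary gives the consequence: "If the subject does not achieve at least a 75% reduction in FI, they are randomized to one of two therapies: BIO or INJ". Section 3.0 (items 2 and 8) keeps end-of-EMM responders on EMM and offers randomization to those who have lost response at 3 months.

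Two further coding rules in Section 8.3 bear on the later rates: "Participants who are non-responders to EMM at 3 months will continue to be classified as non-responders at 6, 12, and 24 months", and "Participants without a valid bowel diary will be classified as non-responders at that time point". Starting FI treatment outside the study also counts as non-response from then on. The paragraph does not name the analysis set, does not say how end-of-EMM non-responders who go on to BIO or INJ are coded at later visits, and promises no sensitivity analysis. Sections 8.1 and 8.2 do promise one for treating missing responses as failures.

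**The concern.** A durability comparison needs a reference that is not fixed by the rule that forms the cohort. Here a patient whose two-week count happened to be low at the end of EMM is labelled a responder and kept on EMM alone. One whose count happened to be high is labelled a non-responder and moved to BIO or INJ. At the next diary the lucky responders can drop back. The unlucky non-responders, who would have balanced them, are no longer on EMM alone. The movement runs one way, and ordinary diary variation looks like loss of effect.

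At stake is the message of Aim E about a low-cost first-line treatment: a reported decline could not be separated from an artifact of selection.

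**Working it through.** **1. The plan's own figure.** Section 5.4: "This leaves 285 to be recruited into the EMM protocol", with 20% expected to respond. 0.20 × 285 = 57, as stated. (The 194 to be randomized in the same section follows only from sequential losses: 285 × 0.85 × 0.80 = 193.8, which implies 285 × 0.85 × 0.20 = 48 responders. With 57 responders and 43 dropouts, 285 − 43 − 57 = 185 remain. These figures need reconciling, but the point here does not turn on them.)

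**2. What each analysis set implies.**
- *End-of-EMM responders only.* The reference is 57/57 = 100%. Its logit is infinite, so the contrast is not estimable, and every later rate is at or below 100%.
- *All EMM starters, randomized non-responders kept as failures.* The reference is 57/285 = 20%. Responders can be lost. The only possible gains are EMM non-responders who were never randomized (Section 3.1, Event Windows), and no number is given for them.

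**3. Size with no true loss.** The documents give no diary variability, so these inputs are assumptions shown as ranges:
- True baseline rates are log-normal (log-scale SD 0.6), mean 4, 7 or 12 episodes per week.
- The ratio of the true on-EMM rate to baseline is logit-normal with SD 0.5 to 3, centred so that 20% respond at the end of EMM, and is then held constant.
- Two-week counts are Poisson, or have variance twice the mean.
- The baseline diary has at least 4 episodes (2 per week, Section 5.1).
- Response is a count of at most 25% of baseline.

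| Mean per week | SD of true ratio | Count variance | Responders meeting the rule again at 3 months | Still counted at 6 months with carry-forward |
|---|---|---|---|---|
| 4 | 0.5 | 2 × mean | 34% | 15% |
| 4 | 1.5 | Poisson | 53% | 37% |
| 7 | 1.5 | Poisson | 61% | 47% |
| 12 | 1.5 | Poisson | 69% | 57% |
| 12 | 3 | Poisson | 83% | 75% |

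A further run, also calibrated to 20%, gave 32% to 82% at 3 months and 13% to 74% at 6 months. Taken together, 32% to 83% meet the rule again at 3 months: 0.32 × 57 = 18 to 0.83 × 57 = 47 patients. On the 285 denominator, 20% becomes 18/285 = 6% to 47/285 = 16%.

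**4. Control.** In the same simulations, if everyone stayed on EMM and was counted either way, the rate was 20% at every visit. The fall comes from selection.

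**5. How little is needed.** With losses only, an exact McNemar test on 6 losses and no gains gives p = 2 × 0.5⁶ = 0.031. It stands in here for the model contrast, for which the plan states no alpha.

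**6. Missing diaries alone.** Suppose every responder is perfectly stable and borrow the Section 5.3 attrition, which is stated there for randomized non-responders: 15% from 3 to 12 months and 15% more to 24 months. Then 57 becomes 57 × 0.85 = 48 (85%) at 12 months and 57 × 0.85² = 41 (72%) at 24 months.

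**The case against.** *The plan says compare, not test.* Section 8.3 gives no hypothesis or alpha for this contrast, and objective 6 is an estimation aim. A reader might infer that Aim E will report a statistically significant loss of durability; the documents do not say so. This stands. The estimated difference itself is still displaced, with or without a p-value.

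*The responders-only set is not the natural reading.* A rate to be estimated in objective 6, and planned at 20% of 285, points to all EMM starters. That is fair, and it removes the non-estimable contrast. It does not remove the one-way movement.

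*A sustained-response measure can only fall, and that alone does not make it invalid.* Correct. The defect is narrower: the difference from the first point cannot be read as loss of treatment effect.

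*BIO or INJ benefit credited to EMM.* Because Section 8.3 sets only outside treatment to failure, a reader might infer that response after BIO or INJ will count as EMM response. Nothing plans this. The section models response to EMM, and its carry-forward rule already keeps responders who fail at 3 months as failures. What is missing is a stated coding rule for end-of-EMM non-responders.

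*The size is assumed.* It is. No single percentage is defensible, and the fall would be zero with no within-patient diary variation and no missing diaries. The direction does not depend on the chosen values.

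**Conclusion.** The comparison misleads when followed as written. Under either EMM-only analysis set, the end-of-EMM rate is fixed by the selecting diary and later rates can essentially only be lower, so a decline appears with the true benefit fully maintained. The assumed ranges, calibrated to 20% response, put repeat response among responders at 3 months at roughly 32% to 83% with no true loss. The carry-forward and missing-diary rules lower later rates further. These percentages illustrate the size of the artifact and do not predict the trial's result. They do not show that EMM benefit will in fact last; they show that this contrast cannot tell. Secondary Aim E alone is affected; the randomized comparison of BIO with INJ is not.

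**What to change.** Revise the EMM paragraph of Section 8.3:

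1. Drop the model contrast against the end-of-EMM rate.
2. Define the cohort as end-of-EMM responders. Report the proportion still responding at 3, 6, 12 and 24 months with Wilson 95% intervals, a method the plan already uses. Call it sustained response, and state that the first drop includes regression to the mean from the selecting diary. Restricting the cohort does not remove that part, so the statement is needed.
3. State that response after starting BIO, INJ or SNS is not counted as EMM response.
4. Assess change over time with FI frequency from the 3-month diary onward, using observed data for all end-of-EMM responders, with a stated rule for those who start BIO or INJ. Limiting this to patients still responding at 3 months would recreate the selection.
5. Add sensitivity analyses without the 3-month carry-forward and without counting missing diaries as non-response.

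The cost is wording, a little more analysis, and the loss of a contrast (and any p-value from it) that cannot be interpreted. No new data are needed.

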  - Research objective 8. To estimate the cost of delivering medical treatment and compare to the cost of delivering any of the other two treatments.
- F. Compare the cost effectiveness of two treatments for moderate to severe FI.
  - Research objective 9: To estimate the average cost effectiveness (i.e., cost per quality adjusted life year gained excluding costs that are only for research purposes) among conservative medical management non-responders for the two treatments at 6, 12, 18 and 24 months.

This 4-site geographically dispersed study will identify the most optimal, durable, safe, and inexpensive treatment for moderate to severe FI patients. In addition, this project will demonstrate the efficacy of enhanced medical management of FI, explore the mechanisms of action for the study treatments, and identify the factors that predict the response to treatment. A successful outcome may result in changes to management strategies.

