A secondary endpoint is an analysis of the cost-effectiveness of the two treatments. The metric used for comparing cost-effectiveness is the quality adjusted life years. This calculation requires a health-related quality of life index, i.e., a generic health related quality of life scale that may be used to compare the morbidity-related impact of different disease states. Harvie and colleagues compared three of these health-related quality of life indices in a group of 200 women with fecal incontinence, urinary incontinence, and/or pelvic organ prolapse. The utility indices compared were the Health Utilities Index Mark 3 (HUI-3), the Euro-Qol (EQ-5D), and the Short Form 12 (SF-6). The HUI-3 and the EQ-5D were comparable in terms of their correlation with FI severity scales and their ability to discriminate between women with FI and those without. However, the EQ-5D is the only one that has previously been used to estimate cost-effectiveness for treatment of FI, and it was shown to be able to discriminate between SNS and another surgical treatment for FI.

*4.1.3.1 EuroQol 5D (EQ-5D):* The EQ-5D consists of 5 domains – mobility, self-care, usual activities, pain/discomfort, and anxiety/depression – with three possible responses indicative of severity of impact for each of the 5 single question corresponding to these 5 domains. It shows good convergent validity with other standard measures of health utility such as the HUI-3, and is able to discriminate between different treatments for FI. The EQ-5D is the most widely used health utilities instrument for assessing cost-effectiveness. This generic QoL measure will complement the disease-specific Fecal Incontinence Quality of Life Scale.

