## 5.2 Sample Size Estimates

## 5.2.1. Primary Efficacy Outcome

Sample-size calculations are based on the number of patients required to detect a difference of 20% in the proportion of responders because we consider this to be the Minimum Clinically Important Difference (MCID) between groups following treatment. Table 3 shows the sample data used in these calculations, which comes from published pivotal trials for dextranomer and biofeedback. Conservatively assuming an average response rate of 50% across the groups, an alpha of .05 and power of 80% we would need at least 97 patients per group to test for differences of this magnitude between 2 treatment groups. Since the planned analysis will use an intention to treat (ITT) approach in which all participants will have a defined efficacy outcome regardless of study completion, this sample size was not inflated to account for potential drop out.

The data in Table 3 suggest that we have an excellent chance of detecting a difference of 20% and of showing that BIO is superior to INJ in the proposed trial. We should also be able to show significant differences between BIO and the other two treatments for adverse events, estimated cost of care, percent continent, and impact of FI on quality of life (Table 4).

Efficacy Outcome Measure	BIO Heymen 	INJ Graf 	Sample size required per group
Baseline: FI days per week	3.4 (SD=2.1)	4.8	
> 50% decrease (%)	93%	53%	28
> 75% decrease (%)	78%	32%	28
Continent (%)	44%	5.9%	29

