#### Table 5. Assumptions underlying power analysis for medical costs of FIT treatments for 3 months

Performing analysis with an alpha of 0.05 results in a power of 1.0 given that the differences in expected treatment costs are so large.

Analysis of Cost from the Societal Perspective. To perform power calculations for the difference in 3-month societal costs, we added treatment cost estimates provided in Table 5 to 3 month medical and productivity costs associated with FI, adjusted by treatment. Medical and productivity FI costs were taken from Xu. Given lack of data on the extent to which each treatment may impact medical and productivity costs of FI, we incorporated the assumptions outlined below (Table 6). Annual direct and indirect medical costs are estimated to be \$2,562, and annual productivity costs are estimated at \$1,549. We multiplied these costs by 0.25 to estimate 3-month costs.

- BIO was assumed to reduce FI medical costs by 25%, and productivity costs by 0%.
- INJ was assumed to reduce FI medical costs by 50% and productivity costs by 25%.

	Societal Cost	Sample Size	Standard Deviation
BIO	\$1,664	103	2,138
INJ	\$10,973	123	5,448

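### Cost-effectiveness is planned as cost-per-QALY ratios with no joint uncertainty method or dominance rule; the per-arm ratio does not compare BIO with INJ, and the incremental ratio is unstable if the QALY difference is small

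*Combined protocol and SAP*

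**What the plan says.** Aim F is to compare the cost-effectiveness of the two treatments. Under it, research objective 9 (section 1.1) reads: "To estimate the average cost effectiveness (i.e., cost per quality adjusted life year gained excluding costs that are only for research purposes". It applies to patients who did not respond to medical management, "for the two treatments at 6, 12, 18 and 24 months". Section 4.1.3 sets the status: "A secondary endpoint is an analysis of the cost-effectiveness of the two treatments".

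Section 8.3 gives the method. "QALY estimates will be obtained from the EQ-5D; annual QALY measures will be calculated". Two summaries follow: "We will assess the average cost per QALY gained for each intervention and the incremental cost per QALY gained by comparing the interventions", with the interventions "ordered from lowest to highest QALY gains". The explanation of that ordering compares a medium-effectiveness intervention with the lowest, and the highest with the medium, although only BIO and INJ are randomized.

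Section 8.3 names no interval method, willingness-to-pay value, net-benefit quantity or dominance rule for this analysis. Bootstrapping appears only in section 8.1, as one option for testing cost differences.

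**The concern.** There are two separate problems.

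**The average ratio is not a comparison.** It divides an arm's cost by that arm's own QALY gain. Neither arm has an untreated comparator, so the gain is an uncontrolled before-after change. EQ-5D is collected both at Baseline and at Randomize (Table 2), and section 8.3 does not say which is the reference. If it is Baseline, improvement during the medical-management run-in is credited to BIO or INJ. Two such ratios, each with its own denominator, cannot be combined into a BIO versus INJ effect.

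**The incremental ratio has no stated uncertainty.** Section 5.2.3 puts the power for costs at 1.0 "given that the differences in expected treatment costs are so large". With the cost sign effectively fixed, the sign of the ratio depends on the QALY difference. If that difference is small relative to its standard error, the ratio jumps between large negative and large positive values and its interval is unbounded. Ordering by QALY gain does not cure this. The denominator becomes positive by construction, but sampling noise then decides which arm is listed as more effective, and the sign moves to the numerator.

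At stake is whether Aim F ends with an interpretable comparison, or with ratios whose uncertainty is handled by choices made after the data are seen.

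**Working it through.** **1. Reproduce the plan's cost figures (section 5.2.3, Tables 5 and 6).**
- BIO: 3 × 265.45 = $796; SD = 0.5 × 3 × (318.55 − 212.36) = 159 (stated 160).
- INJ: 2 × (281.03 + 4,900) = $10,362 (stated $10,363); SD = 0.5 × 2 × [(337.23 + 6,860) − (224.82 + 2,940)] = 4,032 (as stated).
- Difference from the stated figures: 10,363 − 796 = $9,567. With 103 and 123 patients, SE = √(160²/103 + 4,032²/123) = 364, so power is 1.0 as stated.
- With 97 per arm, SE = √((160² + 4,032²)/97) = 410, giving a 95% range of $8,764 to $10,370.
- Societal: BIO 796 + 0.25 × 2,562 × 0.75 + 0.25 × 1,549 = $1,664; INJ 10,363 + 0.25 × 2,562 × 0.5 + 0.25 × 1,549 × 0.75 = $10,974 (stated $10,973). Difference from the stated figures: $9,309.

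**2. Other cost gaps in the plan.**
- Table 4: 7,408 − 1,435 = $5,973.
- Table 1 ranges: from 3,000 − 2,300 = $700 to 7,408 − 1,235 = $6,173.
- A 24-month treatment-cost gap, using section 5.4's 63 INJ and 17 BIO non-responders, half choosing SNS at $18,450 (section 2.2.3) and half the other arm: INJ adds 31.5 × (18,450 + 796)/97 = $6,250; BIO adds 8.5 × (18,450 + 10,363)/97 = $2,525; the gap becomes 9,567 + 6,250 − 2,525 = $13,292.

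The size varies, but INJ is dearer throughout.

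**3. QALY side.** The documents give no EQ-5D or QALY difference and no SD. I assume a one-year QALY SD of 0.10 to 0.25 and 97 per arm, unadjusted.
- SE = SD × √(2/97) = 0.014 to 0.036.
- Chance that the estimated difference has the wrong sign, Φ(−|d|/SE), and the observed difference needed for a bounded 95% Fieller interval, 1.96 × SE:

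| SD | SE | Wrong sign, true d = 0.01 | d = 0.02 | d = 0.05 | Bounded only above |
|---|---|---|---|---|---|
| 0.10 | 0.014 | 24% | 8% | <0.1% | 0.028 |
| 0.15 | 0.022 | 32% | 18% | 1% | 0.042 |
| 0.20 | 0.029 | 36% | 24% | 4% | 0.056 |
| 0.25 | 0.036 | 39% | 29% | 8% | 0.070 |

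With the 78 and 92 expected at 3 months, the thresholds become 0.030 to 0.075.

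**4. What a sign change means.** Take 9,567/0.01 = $956,700 per QALY. If BIO gains 0.01 more, the ratio is −$956,700 and BIO dominates. If INJ gains 0.01 more, INJ costs $956,700 per extra QALY. At illustrative thresholds of $50,000, $100,000 and $150,000 (assumed), INJ breaks even only at gains of 9,567/50,000 = 0.19, 0.096 and 0.064 QALY. Both results therefore favor BIO.

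**5. Net benefit on the same inputs.** The incremental net benefit of INJ is λ × ΔQALY − Δcost. With no true QALY difference, SD 0.20 and λ = $100,000, it is −$9,567. Taking costs and QALYs as independent, SE = √((100,000 × 0.0287)² + 410²) ≈ 2,900, so the 95% range is about −$15,250 to −$3,880. It is finite and has a clear sign. Simulated incremental ratios under the same inputs had 2.5 and 97.5 percentiles of about −$5.4 million and +$5.2 million.

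**6. Where the ratio behaves.** With a true INJ gain of 0.08 QALY and SD 0.10, the simulated 95% range is about $87,000 to $186,000 per QALY, an ordinary interval.

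**The case against.** The strongest reply has four parts.

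- **The instability is conditional.** It needs a small QALY difference relative to its SE. At 0.05 the wrong-sign risk is about 8% or less, and baseline EQ-5D adjustment would shrink the SE further. This stands: a reader might infer that the ratio has no usable interval, but the documents do not establish that.
- **The plan has no QALY input.** A reader might infer that its own figures leave the sign of the QALY difference open. Section 5.2.1 speaks of an excellent chance "of showing that BIO is superior to INJ in the proposed trial" on incontinence response, while Table 4's quality-of-life row is larger for INJ (27.3% against 11.9%). These are proxies from separate trials. The Table 4 row names no scale and gives no SD for INJ, and neither figure is an EQ-5D forecast. The sign is simply not addressed.
- **A wrong sign is not a wrong decision.** This also stands. If BIO truly gains 0.02 and the SE is 0.036, the estimate passes the $150,000 break-even for INJ in only Φ(−(0.064 + 0.02)/0.036) ≈ 1% of trials. The inference that Aim F cannot be answered is therefore not supported.
- **Cost per QALY is a standard metric, the average ratio is what objective 9 requests, and the three-way wording looks like a remnant of SNS leaving the randomization in version 7.0.** All fair. The average can stay as description, but it does not deliver the comparison in Aim F.

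The $9,567 is also a 3-month payer cost, whereas objective 9 starts at 6 months, after non-responders may add treatment. None of these replies supplies the missing interval method or dominance rule.

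**Conclusion.** The concern holds in a limited form. As written, section 8.3 and objective 9 would produce per-arm ratios that do not compare the treatments, and an incremental ratio with no measure of joint cost and QALY uncertainty and no rule for dominance. All the plan's cost figures make INJ dearer, so the behavior of the ratio depends on a QALY difference that the plan never quantifies. Wrong-sign risk is 8 to 29% at a true difference of 0.02 and about 8% or less at 0.05; the interval is unbounded unless the observed difference exceeds about 0.03 to 0.07 QALY.

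Those figures rest on an assumed one-year SD of 0.10 to 0.25 with 97 per arm, and on no covariate adjustment. They describe instability of the ratio, not the rate of wrong conclusions. Because the endpoint is secondary, this is a worthwhile, inexpensive improvement of modest priority.

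**What to change.** In section 8.3, with objective 9 aligned:

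- Make the BIO versus INJ comparison the incremental net monetary benefit as randomized, at prespecified willingness-to-pay values (for example $50,000, $100,000 and $150,000 per QALY) and at the objective 9 time points.
- Adjust for site, sex and pre-randomization EQ-5D, stating which EQ-5D assessment is the reference.
- Resample costs and QALYs together by patient for a bootstrap 95% confidence interval, and plot an acceptability curve.
- Report the incremental ratio alongside only when the cost and QALY differences have the same sign; otherwise state dominance.
- Keep any per-arm average ratio as descriptive only.
- Replace the lowest, medium and highest wording with the single two-arm comparison.

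The cost is a revision of the text, including a small clarification to objective 9. The data are already scheduled for collection. The one real burden is agreeing willingness-to-pay values before the data are seen.
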